Secondary Aim: To describe the effects of fenofibrate monotherapy on lipoprotein particle number and size by nuclear magnetic resonance spectroscopy performed in non-responders and responders at 2 months of treatment, when drug treatment will be discontinued for lack of efficacy to agent. Lipids in responders and control groups will be studied by NMR spectroscopy at 4 months of treatment, which will be at the termination of the proposed treatment period.

Tertiary Aim: To determine the safety of fenofibrate monotherapy. Documentation and description of adverse events will be obtained in subjects who have received drug treatment compared to events occurring in the control group.

Target Population

It is estimated that approximately 100 participants with SCI will be screened to identify 30 eligible and appropriate SCI participants (i.e., 20 treatment, 10 control) who will agree to participate in the study (Screening data from BAU-11-075 will be used to minimize the number of procedures performed, if it is not older than 45 days). To be considered eligible for the study, participants must meet the following eligibility criteria:

Inclusion Criteria:

- (1) Male or female, age 21 to 69;
- (2) Chronic (e.g., duration of injury at least 6 months), stable SCI (regardless of level of neurological lesion);
- (3) American Spinal Injury Association Impairment Scale (AIS) designation of A, B or C; and
- (4) TG concentration ≥ 135 mg/dl (paraplegia) or ≥ 115 mg/dl (tetraplegia).

Exclusion Criteria (These exclusion criteria were carefully chosen to minimize subject risk and/or confounding factors that are known to affect study endpoints):

- (1) Acute illness or infection;
- (2) Reduced kidney function (by glomerular filtration rate (GFR < 60 ml/min) or liver function tests (LFTs ≥ 2.5 times above the upper limit of normal) as determined by test results at screening and any time point of the study;
- (3) Current pharmacological treatment with: HMG-CoA reductase inhibitors (statins), or any other hypolipidemic agent; anti-coagulant therapy; cyclosporine; or any other medications known to effect the TG concentration (i.e., β -blockers, thiazides or estrogen);
- (4) Hypersensitivity to fenofibrate;
- (5) Existing diagnosis of atherosclerosis, congestive heart failure, or recent history of myocardial infarction (i.e., ≤ 12 months);
- (6) Pregnancy or women who may become pregnant during the course of the study, or those who are nursing;

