The proposed investigation is an open-label, parallel-group intervention and randomized trial to determine the safety and efficacy of fenofibrate monotherapy on the lipoprotein profile in persons with SCI. A screening visit will be performed in up to 100 persons with SCI to identify 30 subjects who have adverse TG concentrations (i.e., paraplegia: ≥ 135 mg/dl; tetraplegia ≥ 115 mg/dl). After a baseline evaluation, a comprehensive medical history review and intake interview will be performed to identify demographic information, current health status, medications and lifestyle habits (i.e., smoking, alcohol consumption, recreational drug use, physical activity habits, diet etc.). Twenty subjects with adverse TG concentrations will be randomized to receive once daily fenofibrate therapy (i.e., 145 mg) for 4 months (dispensed by the research pharmacy of the James J. Peters VA Medical Center) and the remaining 10 subjects with adverse TG concentrations will receive no treatment and will serve as control subjects. All subjects will complete monthly follow-up visits for the study period, which also includes a 1-month post-treatment visit. If after 2 months of continuous fenofibrate treatment a subject does not demonstrate an improvement of $\geq 25\%$ in TG concentration, then he/she will be discontinued from the study drug under appropriate supervision and terminated from the study. For those who respond to fenofibrate treatment, he/she will continue on treatment for an additional 2 months.

The primary study outcome will be to determine the efficacy of treatment on the serum lipoprotein profile (i.e., TG, HDL-C, LDL-C, total cholesterol), and the secondary study

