Separate analysis of variance (ANOVA) will be performed to identify group differences (i.e., control, treatment) for baseline demographic data [e.g., age, height, weight, BMI, duration of injury (DOI)]. Pearson chi-square tests will be performed to identify differences for the number of enrolled participants in each group based on gender (e.g., male, female), injury level (e.g., paraplegia, tetraplegia), AIS level (e.g., A, B, C), and ethnicity (e.g., African American, White, Hispanic). Separate 2 (group: treatment, control) X 3 (visit: baseline, Mo2, Mo4) mixed-model repeated measures ANOVA (RMANOVA) will be performed to determine if differences were present for serum lipoprotein profile [e.g., HDL-C, LDL-C, VLDL-C, TG, TC], glucose, insulin, and the TG/HDL-C, LDL-C/HDL-C and TC/HDL-C ratios. Separate

factorial ANOVA will be performed to identify the presence of group differences in the percent change from baseline to 2 and 4 months, respectively in the serum TG, HDL-C, and LDL-C. The nature of significant group or time main effects will be explored with Tukey *post hoc* tests. Although not part of the primary analysis, results from the venous blood samples at months 1 and 3 visits will be provided. Statistical analyses will be completed using IBM SPSS Statistics 25 (IBM, Armonk, NY) and figures will be created with GraphPad Prism (version 8.0 for Windows, GraphPad Software, San Diego, CA). An *a priori* level of significance was set at $p \leq 0.05$.

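### Injury level sets the TG entry limit, but no stratification by it is described and no lipid model names it; chance imbalance is likely enough with 10 controls to justify a cheap fix, though its consequence is modest

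*Combined protocol and SAP*

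**What the plan says.** **Eligibility.** Target Population, inclusion criterion 4, requires "TG concentration ≥ 135 mg/dl (paraplegia) or ≥ 115 mg/dl (tetraplegia", and Methods repeats both limits. They are 20 mg/dl apart. Criterion 2 admits chronic "stable SCI (regardless of level of neurological lesion", with no quota or expected mix of the two levels.

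**Allocation.** Target Population plans to "identify 30 eligible and appropriate SCI participants (i.e., 20 treatment, 10 control". Methods says "Twenty subjects with adverse TG concentrations will be randomized to receive once daily fenofibrate therapy" and that the other 10 serve as untreated controls. No strata, blocks or minimisation are described. The only mention of stratification, under Procedures (Additional Outcomes), concerns ApoE genotype and outcomes.

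**Analysis.** In Statistical Analyses, "Pearson chi-square tests will be performed to identify differences for the number of enrolled participants in each group" on several characteristics, including "injury level (e.g., paraplegia, tetraplegia". No action on the result is stated. The lipid outcomes are analysed by "Separate 2 (group: treatment, control) X 3 (visit: baseline, Mo2, Mo4) mixed-model repeated measures ANOVA (RMANOVA". In addition, "factorial ANOVA will be performed to identify the presence of group differences in the percent change from baseline to 2 and 4 months". Neither model names injury level, although the factors of the second are not fully listed.

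**The concern.** By giving the two levels different entry limits, the plan treats injury level as related to TG, which is the basis of the responder definition and part of the primary outcome. One would expect such a factor to be balanced at randomisation, adjusted for in the analysis, or both. The text describes neither. With 10 controls, each person is 10 percentage points of the comparison arm, so a few chance assignments can make the arms visibly different on this factor.

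If TG change over time or response to drug differs by level, an uneven draw mixes that difference with the drug effect. Even if neither differs, leaving out a factor related to the outcome can cost precision in a very small trial. The baseline chi-square test neither prevents imbalance nor adjusts for it.

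**Working it through.** The plan gives no imbalance probability, effect size or standard deviation, so there is no figure of its own to reproduce.

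**Inputs.** 30 participants, 20 treated and 10 control (Target Population). *Assumption:* K of the 30 have tetraplegia, with K from 10 to 20 as the main range and K from 6 to 24 as the wider one.

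**Formula.** Let X be the number with tetraplegia among the 10 controls. With fixed arm sizes and no stratification, X is hypergeometric:

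P(X = x) = C(K, x) · C(30 − K, 10 − x) / C(30, 10)

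gap = |X/10 − (K − X)/20| = |3X − K| / 20

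**Worked case, K = 15.** A gap of 25 points or more needs |3X − 15| ≥ 5, so X ≤ 3 or X ≥ 7. P(X = 0, 1, 2, 3) = 0.0001, 0.0025, 0.0225, 0.0975. By symmetry the chance is 2 × 0.1226 = 0.245.

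**All mixes (symmetric in the two levels).**

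| K of 30 | P(gap ≥ 25 points) | P(gap ≥ 30 points) |
|---|---|---|
| 6 or 24 | 0.141 | 0.141 |
| 7 or 23 | 0.181 | 0.064 |
| 8 or 22 | 0.210 | 0.078 |
| 9 or 21 | 0.204 | 0.204 |
| 10 or 20 | 0.231 | 0.101 |
| 11 or 19 | 0.246 | 0.108 |
| 12 or 18 | 0.235 | 0.235 |
| 13 or 17 | 0.255 | 0.119 |
| 14 or 16 | 0.260 | 0.122 |
| 15 | 0.245 | 0.245 |

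The chance of a gap of 25 points or more is therefore 23-26% for K = 10 to 20, and 14-21% when 20-30% have either level. The 30-point column jumps because only certain gaps are possible: when K is a multiple of 3, the smallest gap above 25 points is 30. The average gap for K = 10 to 20 is about 15-16 points. If arm sizes were left to a 2:1 coin instead of fixed, simulation at K = 10, 12, 15, 18 and 20 gives 19-21% for 25 points or more.

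**What the chi-square would flag.** For 3/10 v 12/20, a 30-point gap:

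χ² = 30 × (3×8 − 7×12)² / (10 × 20 × 15 × 15) = 30 × 3600 / 45000 = 2.4, p = 0.12

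At K = 15 the test reaches p ≤ 0.05 only for X ≤ 2 or X ≥ 8, with probability 2 × 0.0251 = 0.050. As a share of trials with a gap of 25 points or more, this is 0.050/0.245 = 20%. For K = 10 to 20 the share is 19-22%. Outside that range it is erratic because few tables are possible: 0.009/0.141 = 6% at K = 6 and 0.078/0.210 = 37% at K = 8.

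**After stratified 2:1 blocks.** With blocks of 3 only, the gap is 0 when K is a multiple of 3 and otherwise at most 10 points (K = 16: 6/10 v 10/20). With mixed blocks of 3 and 6, an unfinished block of 6 can leave a larger gap. The worst case with final arms of 20 and 10 is 20 points (K = 16, X = 4: |12 − 16|/20 = 0.20). Either way, no gap reaches 25 points.

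**The case against.** The strongest objection is that the planned analyses are referenced to baseline. Baseline is a visit in the repeated-measures model, percent change is analysed separately, and response is a within-person reduction. A constant TG difference between levels cancels from the group-by-visit contrast. If proportional response is the same in both levels, it adds nothing to percent change either. This stands, and it limits the harm considerably.

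A reader might multiply an imbalance by the 20 mg/dl between the entry limits and set the product against the 25% reduction that defines response. The documents do not support that comparison. It sets a shift in level against a change, and the gap between two entry floors is not the mean TG difference among those enrolled, which is unknown.

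A reader might also infer that the drug comparison is biased, or that response is known to differ by level. Different entry limits say nothing about different response, and the documents give no figure for it. Chance imbalance under randomisation is not systematic bias, and the standard error already allows for it.

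Three further limits stand. The one-in-four figure depends on an assumed mix. A strict 30-point criterion gives only 10-12% for most mixes from one third to two thirds. The chi-square is not powerless: for K = 6 to 24, every gap of 40 points or more with probability above 0.001 gives p ≤ 0.038. What it misses is mostly gaps of 25 to 35 points.

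Finally, the protocol says only that participants are randomised. Stratification is not described, which is not proof that none was used.

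The objection does not remove the remaining risk. Percent change and the baseline visit do not absorb drift or response that differs by level, and the plan names no analysis that would show it.

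**Conclusion.** The point holds as a worthwhile design and efficiency improvement, not as an error that invalidates the trial. The plan makes injury level set TG eligibility, then describes no use of it in allocation and names it in no lipid model.

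Under unstratified 20 v 10 allocation, with one third to two thirds having tetraplegia, about one trial in four (23-26%) would have arms 25 or more points apart on injury level, and the planned test would flag about one in five of those. At 20-30% of either level the chance is 14-21%. The mix is an assumption throughout.

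The consequence is lost precision and possible mixing of level-specific drift or response with the drug effect. For example, a 25-point gap carries one quarter of any untreated difference in change between the levels into the comparison of arms. The documents do not say whether such a difference exists, so the resulting error cannot be sized.

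**What to change.** 1. **Randomisation.** Allocate 2:1 separately within paraplegia and tetraplegia, from a concealed list with randomly mixed blocks of 3 and 6.
2. **Models.** Prespecify injury level as a factor in the percent-change models. In the repeated-measures models, include it together with its interaction with visit. Keep these terms whatever the chi-square shows.
3. **Reporting.** Give baseline counts of injury level by arm, and do not use the test to judge balance.

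If enrolment has started, only items 2 and 3 apply.

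**Cost.** Injury level is already collected. The percent-change models lose 1 degree of freedom. The repeated-measures models lose 1 for level and (2 − 1) × (3 − 1) = 2 for level by visit. Small blocks make allocation somewhat more predictable in an open-label trial, which is the reason for mixing sizes. Unfinished blocks could leave the final split up to two participants away from 20 and 10.

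**Limits.** The model terms adjust for level differences in TG and drift common to both arms. They do not estimate a separate drug effect by level, which 10 controls divided between two levels could hardly support. Nor does the fix address the selection caused by terminating treated non-responders at month 2. That selection can change the treated arm's mix by month 4 even from a balanced start.

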Safety Labs: Serum blood specimen will be obtained for the determination of the glomerular filtration rate (GFR). If at screening or during the trial, GFR is <60 ml/min, the potential subject will not be eligible to enroll in the study, or if the GFR should fall to <60 ml/min during the trial, the participant will be discontinued from study drug; renal function will be monitored for a period of at least 4 months after identifying a fall in creatinine clearance while on study drug. Liver function tests [i.e., AST, ALT (<35 IU/L), GGT (elevated for respective age and

gender)] and complete blood count with differential (CBC with diff) will be obtained and evaluated for abnormal values. If evidence for abnormal liver function (i.e., 2 standard deviations above the upper limit of normal) or infection (white blood cell >10,000 cells/ml), the subject will either be considered ineligible for the study at the time of screening or discontinued from study drug under appropriate supervision and monitored for a period of at least 4 months. These specimens will be processed by a commercial laboratory at the time of collection (LabCorp). All safety labs will be reviewed by [name] (Co-Investigator and study physician). He will be responsible for the oversight of safety monitoring, eligibility and review of all laboratory data from screening and treatment.

Primary Study Outcomes: Venous blood samples will be obtained after an overnight fast (minimum 8 hours) for the determination of lipoprotein concentrations (i.e., HDL-C, LDL-C, VLDL-C, TG and total cholesterol) and lipoprotein particle number and size (i.e., mean size of HDL, LDL and VLDL particle; the number of HDL, LDL and VLDL for the respective sub-fraction of small, medium and large particles). Lipoprotein concentrations will be processed by a commercial laboratory at the time of collection (LabCorp); lipoprotein particle number and size will be performed as a fee-for-service by Liposcience, Inc (Raleigh, NC, USA).

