The health risks associated with this research study are minimal in nature. As with any investigational study, there may be adverse events or side effects that are currently unknown. In the case of a serious adverse event during the test, hospital emergency personnel will be summoned over telephone by study personnel. The following list contains potential risks/and or discomfort related to study procedures:

-Fenofibrate: Common side effects for treatment include abdominal pain, skin rash, and nausea. Less common side effects include gas, bloating, change in bowel frequency and stool color. As mentioned previously participants are at risk to develop elevated and/or abnormal liver and kidney function from taking Fenofibrate. If abnormal levels become evident as indicated by safety monitoring labs taken at each time point, the subject will be discontinued from study drug and monitored on a monthly basis for up to four months or until liver function returns to normal. In addition, if the subject develops elevated and/or abnormal liver function results, they may experience the following: yellowing of eyes/skin, dark urine, pruritis, swelling, and headache.

-Blood draw/catheter placement: The subject may experience the feeling of being lightheaded, dizzy, blurry eyesight, nausea and/or syncope during the needle/catheter insertion. There is also the potential risk of developing a bruise or infection at the site of skin puncture.

-Oral glucose tolerance test: In addition to the listed risks for blood draw/catheter placement, the ingestion of a large volume of glucose may cause some individuals to experience nausea.

-Dual energy x-ray absorptiometry scans: To complete the scan, participants will be asked to transfer from their wheelchair to the scanning bed. This will be completed independently or with assistance from an overhead patient lift. The scan will take approximately 15 minutes to complete during which the subject will be asked not to move. Each dual energy x-ray absorptiometry scan will expose the subject to 8.62 μ Sv of radiation (i.e., equivalent to 1/5 of an average chest x-ray), thus each subject will receive 17.24 μ Sv for the two scans.

Statistical Analyses

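### Exclusion criterion (2) and Safety Labs set different liver-test limits for overlapping decisions, one of them cannot be calculated, and the rules for monitoring after stopping also disagree

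*Combined protocol and SAP*

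**What the plan says.** Three places in the combined protocol and SAP deal with abnormal liver tests.

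- **Target Population, exclusion criterion (2).** The limit is a multiple of ULN: "LFTs ≥ 2.5 times above the upper limit of normal) as determined by test results at screening and any time point of the study".
- **Procedures, Safety Labs.** The limit is in SD units: "If evidence for abnormal liver function (i.e., 2 standard deviations above the upper limit of normal". The consequence is that "the subject will either be considered ineligible for the study at the time of screening or discontinued from study drug". The tests are introduced as "Liver function tests [i.e., AST, ALT (<35 IU/L), GGT (elevated for respective age and" gender. The only figure is the 35 IU/L, and no SD is given for any of the three enzymes. After stopping for a liver abnormality the participant is "discontinued from study drug under appropriate supervision and monitored for a period of at least 4 months". A separate renal rule says "renal function will be monitored for a period of at least 4 months after identifying a fall in creatinine clearance while on study drug".
- **Potential Risks, Fenofibrate.** This section states that "participants are at risk to develop elevated and/or abnormal liver and kidney function from taking Fenofibrate". It gives the trigger without any limit: "If abnormal levels become evident as indicated by safety monitoring labs taken at each time point, the subject will be discontinued from study drug". It then describes monthly monitoring that lasts no more than four months, or ends when liver function is normal again.

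**The concern.** Exclusion (2) and Safety Labs cannot be separated into an entry rule and a stopping rule. Both apply at screening, and both reach results obtained during the trial. Safety Labs introduces its limit as a definition, not an example. A reader therefore has two definitions of the same thing on different scales, with nothing to rank them, and one lacks the quantity needed to apply it.

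These rules decide who enters and who keeps taking a drug that the protocol itself says can disturb liver and kidney function. For a result between the two limits, the decision depends on which section is followed and which SD the reader supplies. The wording on monitoring after stopping has a similar but smaller problem.

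**Working it through.** The plan has no figure of its own to reproduce. The check sets the sections side by side and puts both limits on one scale.

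**Inputs**

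- Exclusion (2): 2.5 times ULN. Read literally, 2.5 times *above* ULN is ULN + 2.5 × ULN = 3.5 × ULN.
- Safety Labs: ULN + 2 SD, with SD not stated.
- ULN = 35 IU/L for ALT. This is an assumption, taken from the 35 IU/L printed after ALT in Safety Labs.
- SD: assumed values only. Because the scale is not stated either, raw and log scales are both shown.

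**Exclusion (2) limit**

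- 2.5 × 35 = 87.5 IU/L
- Literal reading: 35 + 2.5 × 35 = 122.5 IU/L

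**Safety Labs limit**

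| Assumed SD | Calculation | Limit (IU/L) | Multiple of ULN |
|---|---|---|---|
| raw, 5 | 35 + 2 × 5 | 45 | 1.29 |
| raw, 8.75 | 35 + 2 × 8.75 | 52.5 | 1.50 |
| raw, 17.5 | 35 + 2 × 17.5 | 70 | 2.00 |
| log, 0.3 | 35 × exp(0.6) | 63.8 | 1.82 |
| log, 0.6 | 35 × exp(1.2) | 116.2 | 3.32 |

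**Where the limits cross**

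- Raw scale: ULN + 2 SD = 2.5 × ULN gives SD = 0.75 × ULN = 26.25 IU/L (43.75 for the literal reading).
- Log scale: SD = ln(2.5)/2 = 0.458 (ln(3.5)/2 = 0.626 for the literal reading).

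**A bound.** Suppose ULN is itself the reference mean plus 2 SD, with a non-negative mean (assumption). Then SD ≤ 35/2 = 17.5, and the Safety Labs limit is at most 70 IU/L, or 2.0 × ULN. Safety Labs is then always the lower limit. An ALT above 70 and below 87.5 IU/L would make a participant ineligible, or stop the drug, under Safety Labs without being caught by exclusion (2). On a log scale the bound does not apply: at SD 0.6 the limit is 116.2 IU/L, above 87.5 but still below the literal 122.5.

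**Monitoring after stopping for a liver abnormality**

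- Safety Labs: four months is a minimum.
- Potential Risks: four months is most naturally a maximum, with an exit on recovery.

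The two durations agree only at exactly four months. A participant whose tests normalise after one month could leave monitoring under Potential Risks but not under Safety Labs. Potential Risks also covers kidney abnormalities in the same sentence but ends monitoring on liver recovery alone, unlike the renal rule in Safety Labs. Table 2 does not settle this, because it schedules a single visit one month after treatment.

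**Comparison with kidney.** The GFR limit of 60 ml/min is the same in exclusion (2) and Safety Labs, so the threshold conflict is confined to the liver tests.

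**The case against.** The strongest reply is that the two limits differ but do not exclude each other. A participant can be checked against both, breaching either is enough, and one study physician reviews all safety labs and eligibility. Consistent judgement by one person is a real protection. But it does not supply the missing SD, and applying both limits, or the stricter one, is impossible while one of them cannot be calculated.

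It is also fair that exclusion (2) sits in an eligibility list and does not itself say that drug is stopped. Its reach to on-treatment results comes only from its reference to later time points. The contradiction is therefore firmest at screening. During treatment the plainer defect is that the stopping limit in Safety Labs has no SD.

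Potential Risks may be only a recap, and a risk summary need not carry a numeric limit. That is accepted, though the recap points to neither definition. On monitoring, following the Safety Labs minimum would cover participants who recover early, and its renal rule covers the kidney, so this part is secondary.

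Finally, the SDs are assumed, and the protocol never mentions a log scale. The figures show only how far the answer moves with an input the protocol leaves out; the finding does not rest on them.

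**Conclusion.** The concern holds and needs correction. The liver limits conflict for overlapping decisions, and the one with an explicit stopping action cannot be calculated as written. Neither conclusion needs an assumption.

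The size of the gap does. With ALT ULN at 35 IU/L and raw-scale SDs of 5 to 17.5, it is 17.5 to 42.5 IU/L against the 87.5 reading (87.5 − 70 and 87.5 − 45). With a log-scale SD above about 0.46 the order reverses against that reading. The documents do not allow the number of participants affected to be estimated.

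The monitoring mismatch is real but secondary, and matters when liver tests normalise early. No effect on the primary analysis is claimed.

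**What to change.** Reconcile exclusion (2), Safety Labs and Potential Risks:

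1. State one liver threshold, on one scale that can be applied directly to the laboratory's reports, in identical words in exclusion (2) and Safety Labs. Each section already uses a single limit for screening and on-study results. If the sponsor in fact intends different limits for entry and for stopping, the text should say so and make each one computable.
2. If a multiple of ULN is used, word it so that it has only one reading. If SDs are used, give the SD, its source and its scale for each enzyme.
3. Say what action follows a breach at screening and what follows one during the study.
4. State one monitoring duration for liver and one for kidney, and use them in both sections.
5. Have Potential Risks refer to the Safety Labs definitions.

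The values are for the study physician to choose; none is proposed here. The cost is a short wording amendment to three sections, with no additional participants and no change to the statistical analysis.

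### Exclusion criterion (2) runs past randomisation on a variable that fenofibrate can affect, and nothing in the plan secures these subjects a place in the triglyceride comparison

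*Combined protocol and SAP*

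**What the plan says.** - **Target Population, exclusion criterion (2).** The criterion applies "as determined by test results at screening and any time point of the study". Its kidney limit is a GFR below 60 ml/min, and its liver limit is given as "liver function tests (LFTs ≥ 2.5 times above the upper limit of normal". Criterion (9), by contrast, ties its laboratory thresholds for diabetes to the screening blood tests.
- **Procedures, Safety Labs, kidney.** The sentence opens "If at screening or during the trial, GFR is <60 ml/min, the potential subject will not be eligible to enroll in the study". It then adds that "if the GFR should fall to <60 ml/min during the trial, the participant will be discontinued from study drug", and asks for renal function to be monitored for at least 4 months.
- **Procedures, Safety Labs, liver.** The limit here is 2 standard deviations above the upper limit of normal. A subject who crosses it is ineligible if this is found at screening; otherwise the subject is "discontinued from study drug under appropriate supervision and monitored for a period of at least 4 months".
- **Potential Risks, Fenofibrate.** The section states that "participants are at risk to develop elevated and/or abnormal liver and kidney function from taking Fenofibrate". The stated action is to stop study drug and monitor monthly, for up to four months or until liver function is normal again.
- **Target Population and Methods.** Allocation is "20 treatment, 10 control", and "the remaining 10 subjects with adverse TG concentrations will receive no treatment and will serve as control subjects".
- **Methods.** All subjects are to complete the monthly visits. Removal from the trial is spelled out only for treated subjects whose TG has not improved by at least 25% at 2 months.
- **Statistical Analyses.** The model is a 2 (group) by 3 (baseline, Month 2, Month 4) repeated measures ANOVA. No analysis set and no rule for missing visits is given.

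**The concern.** An eligibility criterion should act before randomisation. This one continues afterwards and depends on laboratory values that the protocol itself says the drug can change, while controls take no drug. If the criterion is applied as written, leaving the trial depends partly on treatment. Month 2 and Month 4 TG would then be compared between groups that are no longer the randomised ones.

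The sections that describe on-study handling point another way, towards stopping drug and monitoring. The protocol therefore gives two answers for the same subject, and the analysis section does not choose between them. A subject stopped at Month 1 for a laboratory value has not completed 2 months of continuous treatment, so is neither a responder nor a classified non-responder. The aims give that subject no place in the Month 2 responder percentage, or among the responders and controls whose lipids are profiled at Month 4.

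**Working it through.** **1. The sections side by side**

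| Place | Liver limit | Consequence if crossed on study | Lipid follow-up stated? |
|---|---|---|---|
| Exclusion criterion (2) | 2.5 times above upper limit | Exclusion criterion met | No |
| Safety Labs, kidney | not applicable | Eligibility clause extends to on-trial results; next clause stops study drug | No, renal monitoring only, at least 4 months |
| Safety Labs, liver | 2 SD above upper limit | Study drug stopped | No, monitoring unspecified, at least 4 months |
| Potential Risks | abnormal, no figure | Study drug stopped | No, monthly monitoring, up to four months or until liver function is normal |

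The sections disagree on the consequence, the liver limit and the length of follow-up.

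**2. Which arm would lose subjects**

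The documents give no kidney or liver event rate, so there is no figure of the plan's to reproduce beyond 20 + 10 = 30. Let pT and pC be the probabilities of crossing a limit in the fenofibrate and control arms (assumed values), and RR = pT/pC.

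- Expected numbers crossing: 20·pT and 10·pC.
- Fenofibrate share: 20·pT / (20·pT + 10·pC) = 2·RR / (2·RR + 1).

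| Assumed pT, pC | Expected, fenofibrate | Expected, control | Fenofibrate share |
|---|---|---|---|
| 5%, 5% | 1.0 | 0.5 | 1.0/1.5 = 67% |
| 10%, 5% | 2.0 | 0.5 | 2.0/2.5 = 80% |
| 20%, 5% | 4.0 | 0.5 | 4.0/4.5 = 89% |
| 10%, 2% | 2.0 | 0.2 | 2.0/2.2 = 91% |
| 10%, 1% | 2.0 | 0.1 | 2.0/2.1 = 95% |
| 10%, 0% | 2.0 | 0 | 100% |

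For a share s, the rate ratio needed is s / (2(1 − s)): 0.90/0.20 = 4.5 for 90%, and 0.95/0.10 = 9.5 for 95%.

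**3. Chance that the question arises at all**

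P(at least one) = 1 − (1 − p)^n.

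- Fenofibrate arm, n = 20: 1 − 0.95^20 = 64% at an assumed 5%; 1 − 0.90^20 = 88% at 10%.
- Control arm, n = 10: 1 − 0.99^10 = 10% at an assumed 1%; 1 − 0.95^10 = 40% at 5%.

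**4. Illustration for the Month 2 responder percentage**

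Each treated subject is 1/20 = 5% of the arm. Assume 10 of 20 truly respond (50%) and that the subjects removed are either all responders or all non-responders:

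- 2 removed: 8/18 to 10/18, 44% to 56%.
- 3 removed: 7/17 to 10/17, 41% to 59%.
- 4 removed: 6/16 to 10/16, 38% to 63%.

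Both the 50% and the 2 to 4 removals are assumptions, and the ranges are extremes. They describe one arm's percentage, not the between-arm TG difference, and only limits crossed by Month 2 can affect them.

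**The case against.** The strongest reply is that this is loose drafting, not a rule that removes anyone. Safety Labs pairs ineligibility with the potential subject and stopping drug with the participant, and its liver sentence separates screening from on-study cases cleanly. Potential Risks also says stop and monitor. Methods has all subjects complete monthly visits and reserves termination for TG non-responders, so the authors evidently wrote removal where they meant it. The lack of an analysis set is a general gap, not one created by criterion (2).

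Much of this stands. A reader might infer that the plan requires these subjects to leave the trial or the analysis. The documents do not support that: removal is one reading of criterion (2), against two sections that say otherwise.

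The reply does not close the point. Criterion (2) expressly reaches past screening, and the Safety Labs kidney sentence repeats that reach in its eligibility clause. The promise of monthly visits is not absolute, since the same paragraph ends participation for non-responders. No section says that lipids continue to be measured after a safety stop. The general gap in the analysis section matters more here because a stated criterion can be used to drop subjects on a treatment-affected variable.

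Two further inferences also fail:

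- **That nearly all losses would come from the fenofibrate arm.** The criterion does not require the change to be drug-related, and the procedures table does not separate the arms, so controls can meet it too. A 90% share needs an assumed rate ratio of 4.5.
- **That affected subjects drop out of the safety aim.** That aim covers subjects who have received drug, so a subject stopped for a laboratory change still belongs to it.

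**Conclusion.** The point holds in a limited form. Criterion (2) as worded allows exclusion after randomisation on a variable that the drug can affect. It conflicts with the stop-and-monitor text elsewhere, and no analysis set protects the Month 2 and Month 4 TG comparison. If such subjects are lost, most would be expected to come from the fenofibrate arm: 67% at equal rates, from the 2:1 allocation alone, rising towards 100% as the drug raises the rate relative to control.

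The number lost cannot be stated. At assumed rates of 5% to 20% it is 1 to 4 of 20 treated subjects (20 × 0.05 to 20 × 0.20). The direction of any bias is also unknown, because the documents do not link laboratory changes to TG response. The responder ranges of 44–56% to 38–63% are illustrations under assumed inputs, not estimates.

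**What to change.** 1. **Eligibility.** End exclusion criterion (2) after the word screening. In the Safety Labs kidney sentence, delete the words that extend the eligibility clause to results during the trial.
2. **Retention and analysis.** Add a statement such as: *A randomised subject whose kidney or liver tests cross a limit remains in all scheduled lipid visits and is analysed in the assigned group, in the all-randomised efficacy analysis and in the safety tables, whatever is decided about study drug.* Name the all-randomised set in Statistical Analyses, and say how a missing Month 2 or Month 4 value is handled. A complete-case repeated measures ANOVA would drop a subject with either value missing.
3. **Reconciliation.** Criterion (2), Safety Labs and Potential Risks must agree on the on-study liver limit (2.5 times above the upper limit of normal, or 2 standard deviations above it) and on follow-up (at least 4 months, or up to four months or until liver function is normal). Which limit and which stopping rule apply is a clinical choice for the sponsor.

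**Cost.** Protocol wording, and a few scheduled visits for subjects who are already to be monitored for months. The estimated effect will include time off drug, which should be said when it is reported. The change does not address the separate termination of TG non-responders at 2 months, who would still be absent at Month 4.
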